Study Title:

ProAir Digihaler in COPD Disease Management: A real world study to assess ProAir Digihaler inhalation parameters thresholds and their use to identify deterioration in clinical practice

Study Site:

Pulmonary Research Institute of Southeast Michigan between May 19, 2021 and June 20, 2022

Study NCT #: NCT04821869

Advarra IRB Approval: Mar 30, 2021

Title: ProAir Digihaler in COPD Disease Management: A real world study to assess ProAir Digihaler inhalation parameters thresholds and their use to identify deterioration in clinical practice

Primary Investigator: [name].

Teva Collaborating Investigators: [name]., [name]

Background: Despite increasing awareness of the problems and needs, COPD remains the 3rd leading cause of death in the world and has significant impacts on patient function and quality of life. Even in those patients diagnosed with COPD, management is very poor, with over half of COPD exacerbations never reported. In addition, patients who do seek medical attention often delay reporting when they have symptoms of exacerbations. The consequences of these events are well known, with negative impacts on lung function, symptoms, quality of life, future exacerbations and increased mortality. Finding a way to assist patients and caregivers to better identify deterioration in COPD and improve disease management is essential to overcoming these issues.

Proposal:

A pilot study to explore the utilization of the TEVA ProAir Digihaler rescue medication use and inhalation parameters to identify disease deterioration to help in the management of COPD patients in clinical practice.

This study is designed to follow a small sample size of patients with COPD, monitor and collect inhalation parameters from the DIGIHALER dashboard, and changes in symptom control as measured by the COPD Assessment Test (CAT) to identify potential inhalation parameter thresholds that could be applied to the management of patients with COPD in clinical practice.

Objective(s):

Primary Objective:

- 1) Identify trends in Peak Inspiratory Flow (PIF) rates that associate with disease deterioration as defined by loss of symptom control and reduced lung function in patients with COPD.

Secondary Objectives:

- 1) Describe specific changes in ProAir Digihaler PIF (e.g. 10, 20, or 30% reduction in PIF from baseline for a minimum of 2 consecutive days) to identify an optimal threshold for characterizing trends in acute changes in the COPD Assessment Test (CAT)

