- 2) Describe specific ProAir Digihaler SABA inhalations per day (Inhalations) above baseline (e.g. 2, 4 or 6 inhalations/day for a minimum of 2 consecutive days) to identify an optimal threshold for characterizing trends in acute changes in the CAT
- 3) Describe specific changes in ProAir Digihaler Inhalation Volume (IV) (e.g. 10, 20, or 30% reduction in IV from baseline for a minimum of 2 consecutive days) to identify an optimal threshold for characterizing trends in acute changes in the CAT

Exploratory Objectives:

- 1) Determine whether ProAir Digihaler changes in PIF and in SABA use above baseline thresholds are influenced by baseline COPD condition, as measured by:
 - a) COPD Assessment Test (CAT)
 - b) Modified Medical Research Council Dyspnea Scale (mMRC)
 - c) GOLD group [A-D]
 - d) FEV₁ severity/GOLD grade [I-IV]5)
 - e) BODE score [Body Mass Index (BMI), Airway Obstruction (FEV₁), Dyspnea (mMRC), and Exercise Tolerance (6-minute walk)]
- 2) Determine if concomitant measurement of Anthonisen Exacerbation Criteria (dyspnea, sputum amount and color change) using the Breathlessness, Cough and Sputum Survey (BCSS) is associated with ProAir Digihaler changes in PIF below baseline thresholds
- 3) Determine if concomitant measurement of Anthonisen exacerbation criteria (dyspnea, sputum amount and color change) using the Breathlessness, Cough and Sputum Survey (BCSS) is associated with ProAir Digihaler changes in SABA use above baseline thresholds
- 4) Determine if concomitant measurement of Anthonisen exacerbation criteria (dyspnea, sputum amount and color change) using the Breathlessness, Cough and Sputum Survey (BCSS) is associated with ProAir Digihaler changes in Inspiratory Volume below baseline thresholds
- 5) Determine if Inspiratory Capacity (IC) correlates to Inhalation Volume (IV) measured by the ProAir Digihaler, at baseline and during the study

Primary Outcome Measure:

- 1) Change in Peak Inspiratory Flow (PIF) from Baseline as measured via the ProAir Digihaler device

Secondary Outcome Measures:

1. Change in SABA use (Inhalations) from Baseline
2. Change in Inhalation Volume (IV) use from Baseline
3. Change in CAT
4. Change in FEV₁

Other Outcome Measures:

1. Change in Anthonisen Exacerbation Criteria
2. Change in BCSS
3. Change in Inhalation Volume

Trial Population Entry Criteria:**Inclusion Criteria:**

- 1) Documented history of COPD by ATS/GOLD criteria
- 2) Age > 45 years
- 3) Patient willing and able to:

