If a serious adverse event occurs, the Institutional IRB will be notified within five business days of awareness of the event by the investigator. The study coordinator may initiate the IRB notification, but it must be filed by the study investigator or co-investigators. If the serious adverse event is fatal or life threatening, notification to the Institutional IRB must be made within 24 hours, irrespective of the extent of available adverse event information. This timeframe also applies to additional new information (follow-up) on previously forwarded serious adverse event reports.

The MedWatch 3500A form should be utilized to report serious adverse events to the FDA.

All adverse events (serious and non-serious) will be reported on the adverse event page(s) of the CRF. Adverse events should be reported using concise medical terminology on the CRFs. Non-serious AE's will be reported annually to the IRB as appropriate.

STATISTICAL ANALYSIS

Primary Outcome Measure:

- 1) Change in Peak Inspiratory Flow (PIF) from Baseline as measured via the ProAir Dihaler device

Secondary Outcome Measures:

1. Change in SABA use (Inhalations) from Baseline
2. Change in Inhalation Volume (IV) from Baseline
3. Change in CAT
4. Change in FEV₁

Other Outcome Measures:

1. Change in Anthonisen Exacerbation Criteria
2. Change in BCSS
3. Change in Inhalation Volume

All data is exploratory, with no calculated power or expected predictive probabilities. Statistical thresholds, comparisons, correlations and regressions, sensitivity/specificity/ROC analysis will be performed using Wizard 1.9.45 Statistics. Additional statistical analysis may be performed as per TEVA biostatistics.

PLANNED ANALYSIS

1. Average of PIF value and number of PIF events at 10%, 20%, 30%, 40% below Baseline PIF for 2 or more days per patient
2. Average summary statistics PIF values and frequency of PIF events across all patients
3. Number of inhalations per day that are 4 or more Inhalations above Baseline Inhalations for 2 or more days
4. Frequency of IV events that are 20% below Baseline (see Derived measurements) for 2 or more days
4. Frequency of combined events of PIF and IV 20% below Baseline and 4 or more Inhalations per day above Baseline for 2 or more days combined
5. Frequency of CAT events (defined as increase in CAT score by 2 above Baseline CAT score)
6. Correlation and regression analysis of PIF, Inhalations and IV events with CAT events

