7. Correlation and regression analysis of PIF and/or Inhalations events at varying thresholds
 - a. Daily PIF 10, 20, 30 or 40% below Baseline PIF
 - b. Daily Inhalations at 2, 4 or 6 Inhalations above Baseline Inhalations
 - c. Daily PIF and/or Inhalations duration of 2, 3 or 4 or more days outside of Baseline
8. Frequency and duration of AEC events of 2 or more major symptoms (Type I and Type II)
9. Frequency and duration of BCSS events (increase in BCSS by 2 above Baseline BCSS)
10. Correlation and regression analysis of PIF, Inhalations and IV events with AEC events
11. Correlation and regression analysis of PIF, Inhalations and IV events with BCSS event
12. Correlation of Digihaler changes in PIF above baseline and changes in CAT
13. Correlation off changes in SABA use above baseline with changes in CAT
14. Correlation of Digihaler changes in Inhalation Volume above baseline with changes in CAT
15. Descriptive sub-group analysis of PIF, Inhalations and IV thresholds by FEV1 severity, GOLD groups and BODE at Baseline.

REFERENCES

1. World Health Organization. Global Health Estimates 2016: Deaths by Cause, Age, Sex, by Country and by Region 2000–2016. 2018 [accessed October 2020]. s
2. GOLD. Global Strategy for the Diagnosis, Management, and Prevention of Chronic Obstructive Pulmonary Disease. 2020 Report. www.goldcopd.org.
3. Nici L, et al. Pharmacologic Management of Chronic Obstructive Pulmonary Disease. An Official American Thoracic Society Clinical Practice Guideline Am J Respir Crit Care Med. 2020; 201:56-59.
7. van der Molen T, Miravitles M, Kocks JW. COPD management: role of symptom assessment in routine clinical practice. Int J Chron Obstruct Pulmon Dis. 2013; 8:461-471.

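### Planned Analyses 12 and 14 look above baseline for PIF and IV although the protocol's signal is a fall, and IV gets a single cut although its objective asks for the best one

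*Protocol*

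**What the plan says.** Three consecutive items of the Planned Analysis list (Protocol, Statistical Analysis) relate change in a device measure to change in CAT:

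- Item 12, PIF: "Correlation of Digihaler changes in PIF above baseline and changes in CAT".
- Item 13, rescue use: "Correlation off changes in SABA use above baseline with changes in CAT".
- Item 14, IV: "Correlation of Digihaler changes in Inhalation Volume above baseline with changes in CAT".

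The objectives give PIF and IV the opposite direction. Secondary Objective 1 gives as its example a "10, 20, or 30% reduction in PIF from baseline for a minimum of 2 consecutive days", and Secondary Objective 3 uses the same percentages and duration for IV. Secondary Objective 2 looks at a rise in rescue use, "2, 4 or 6 inhalations/day for a minimum of 2 consecutive days". All three aim to find an optimal threshold for acute change in CAT.

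On thresholds, item 1 counts PIF events at four cuts and item 7 varies the cuts for PIF and for inhalations. IV events appear in the two items that are both numbered 4, each time at 20% below baseline.

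Two other sentences touch on thresholds in general terms. The paragraph before the list says "Statistical thresholds, comparisons, correlations and regressions, sensitivity/specificity/ROC analysis will be performed using Wizard 1.9.45 Statistics". Item 15 is a "Descriptive sub-group analysis of PIF, Inhalations and IV thresholds by FEV1 severity" and other baseline groupings.

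**The concern.** There are two separate problems.

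**Direction.** A rise in rescue use signals worsening, so *above baseline* fits item 13. For PIF and IV the protocol's signal is a fall. An analyst who took items 12 and 14 at their word would look at the patient-days on which PIF or IV was higher than baseline and leave out those that the objectives are about. Change in PIF is the primary outcome and change in IV a secondary outcome. These two items are the only listed analyses that relate change in either measure, rather than threshold events, to change in CAT.

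**IV threshold.** Finding an optimal cut requires comparing at least two. The list names one for IV, so it can show whether a 20% fall tracks CAT events but not whether 10% or 30% would do better. That comparison is what Secondary Objective 3 asks for.

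Exploratory Objective 1 has a smaller ambiguity of the first kind: "Determine whether ProAir Digihaler changes in PIF and in SABA use above baseline thresholds are influenced by baseline COPD condition" can be read with *above* covering PIF as well as rescue use.

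**Working it through.** The protocol states no power, alpha or effect size, so there is no figure to reproduce. The check sets the protocol's statements side by side.

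**Step 1: direction.** Places where the direction is unambiguous:

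| Measure | Stated as a fall | Stated as above baseline |
|---|---|---|
| PIF | Secondary Objective 1; Exploratory Objective 2; at-risk rule (Protocol Overview, appears twice, counted once); items 1, second 4 and 7a: **6** | item 12: **1** |
| IV | Secondary Objective 3; Exploratory Objective 4; first and second item 4: **4** | item 14: **1** |

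Exploratory Objective 1 is ambiguous and is not counted. The outcome measures are plain changes from baseline, with no direction. A CAT event (item 5) is a rise of 2, so the relation of interest is a fall in PIF or IV together with a rise in CAT.

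**Step 2: what a literal reading could do.** This is illustration only; none of the values below is in the protocol. Let PIF change and CAT change be bivariate normal with overall correlation ρ and baseline at the centre of the distribution. Keeping only values above baseline gives

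r₊ = ρ√v / √(1 − ρ²(1 − v)), with v = 1 − 2/π = 0.363.

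- ρ = −0.3: −0.3 × 0.603 / √(1 − 0.09 × 0.637) = −0.19
- ρ = −0.5: −0.5 × 0.603 / √(1 − 0.25 × 0.637) = −0.33
- ρ = −0.7: −0.7 × 0.603 / √(1 − 0.49 × 0.637) = −0.51

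If CAT moves with PIF only below baseline, with slope b and unit residual SD, the correlation above baseline is 0. Below baseline it is b√v / √(b²v + 1), which is −0.34, −0.52 and −0.64 for b = −0.6, −1.0 and −1.4. With the full signed change, nothing is lost through truncation. The harm therefore depends entirely on whether the words are applied as a restriction.

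**Step 3: thresholds.** Example cuts in each secondary objective against cuts in the numbered list:

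| Measure | Example cuts in the objective | Cuts in the list | Examples carried over |
|---|---|---|---|
| PIF | 10, 20, 30% | 10, 20, 30, 40% (items 1, 7a) | 3 of 3 |
| Inhalations | 2, 4, 6 per day | 4 (item 3); 2, 4, 6 (item 7b) | 3 of 3 |
| IV | 10, 20, 30% | 20% (both items 4) | 1 of 3 |

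Inhalations shows the pattern the list follows: a single-cut item (3), then a varying-threshold item (7b). IV has the first and not the second.

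**Step 4: the route to CAT.** Item 6 relates PIF, inhalation and IV events to CAT events. PIF events come from item 1 at four cuts, all falls. IV events come from the first item 4 at one cut. So PIF keeps a correctly directed route at several cuts, and IV keeps one at 20% only.

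**The case against.** On direction, the case against is that this is a slip any reader of the whole protocol can resolve. The fall is stated six times to one and four times to one, the outcome measures are unrestricted changes, and nothing says that below-baseline values are dropped. Much of that stands, and it is why no numerical effect is claimed and the figures in Step 2 are illustration only. It does not remove the error. Items 12 and 14 are operative analysis lines, and followed as written they address the wrong side.

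Exploratory Objective 1 can fairly be read with *above* attached to rescue use alone, particularly as Exploratory Objectives 2 and 3 separate the two directions. It is a clarification and no more.

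On IV, the cuts in Secondary Objective 3 are examples, the general sentence plans threshold and ROC work without limiting it to PIF, item 15 speaks of IV thresholds in the plural, and a statistical analysis plan not seen here could add cuts. So it cannot be concluded that no IV search would be done. But the protocol is not silent. It fixes the IV event at 20% and names the two measures whose cuts vary. Neither general sentence supplies a second IV cut or ties one to CAT, and item 15 is descriptive.

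It is also true that item 7 names no outcome, so the counts of 3 of 3 show that cuts reappear in the list, not that each is expressly tied to CAT. For PIF the tie runs through items 1 and 6. For inhalations above 2 or 6 per day it is only implied. IV has no further cuts to tie.

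**Conclusion.** Both parts hold, and both should be corrected; neither undermines the study.

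Items 12 and 14 contradict the direction used everywhere else that the protocol is clear (6 to 1 for PIF, 4 to 1 for IV). This is probably a carried-over phrase. It does damage only if applied as a restriction to rises, and event-based analyses in the right direction remain (items 1, 6 and 7a for PIF; items 4 and 6 for IV).

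The numbered plan does not answer Secondary Objective 3: it carries one of the three example IV cuts, against three of three for each of the other two measures. This rests on the protocol's own list and does not assume that an IV threshold analysis is ruled out elsewhere.

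**What to change.** - **Items 12 and 14:** replace *above baseline* with signed change from baseline, negative meaning a reduction. Leave item 13 as it is.
- **Exploratory Objective 1:** make clear that *above* applies to rescue use only.
- **Item 7:** add Daily IV at 10, 20 and 30% below Baseline IV for 2 or more consecutive days, the duration in Secondary Objective 3. Define Daily IV there as the mean IV over all rescue inhalations in a day, since the Protocol Overview defines only the daily PIF and daily inhalation values. State that, for Secondary Objective 3, the IV cuts are compared against the CAT events of item 5, without confining the rest of item 7 to CAT.

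These are wording changes and use data already collected. The cost is one more set of exploratory analyses, which adds to the number of comparisons in a 20-patient pilot.
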